1.0 PROJECT SUMMARY/ABSTRACT

Premenstrual syndrome (PMS) is an important quality-of-life issue that affects approximately 30% of women. The cause of the disorder is poorly understood. It has been hypothesized that individual gonadal (i.e. ovarian) hormone kinetics - reflecting trajectories of hormone concentration over time - are critical for understanding the etiology of PMS. Another important factor in the etiology of PMS is stress.

The purpose of this study is to thoroughly evaluate how individual hormone kinetics and reactivity to stress contribute to the etiology of PMS. The study will enroll healthy women with regular menstrual cycles. They will chart their symptoms, menstruation timing and ovulation during the **two menstrual cycles while in the study**. This data will form the basis for PMS/PMDD diagnosis. In the **second menstrual cycle**, participants will complete the following study procedures:

- Blood draws and salivary sample collection at 8 different times of the menstrual cycle
- Psychosocial stress testing

[figure not shown]
If the second menstrual cycle is anovulatory, blood draws and salivary sample collection will be repeated in the third menstrual cycle. Knowledge gained from this experiment will increase our understanding of the underlying etiology of PMS.

2.0 BACKGROUND/SCIENTIFIC RATIONALE

Premenstrual syndrome is characterized by the presence of affective and physical symptoms that begin in the late luteal phase of the menstrual cycle and resolve in the early follicular phase. Most women of reproductive

age experience one or more mild emotional or physical symptoms for one to two days before the onset of menses. In contrast, clinically significant PMS is defined as at least one symptom associated with economic or social dysfunction that occurs during the five days before the onset of menses and is present for at least three consecutive menstrual cycles (American College of Obstetricians and Gynecologists). Though women with PMS experience a wide variety of recurrent physical and cognitive symptoms, the core symptoms include affective symptoms, such as depression, irritability, and anxiety, and somatic symptoms, such as breast pain, bloating and headache.

Our study will evaluate reproductive and HPA axis hormonal changes over the course of the menstrual cycle. Study participants with and without PMS/PMDD diagnosis will provide blood and saliva samples at 8 specific, ovulation-guided time points in the menstrual cycle (Figure 1, left side, yellow color). Saliva is collected to measure cortisol levels, as cortisol is a biological marker of stress. Additionally, they will complete the Trier Social Stress Test (Figure 1, middle, green color) to assess how acute stress exacerbates PMS. The main hypothesis is that variability in cyclical reproductive hormone kinetics will

indirectly affect PMS/PMDD diagnosis (Figure 1, right side, teal color) via a single pathway running through cyclical HPA axis hormone kinetics and acute stress reactivity.

3.0 OBJECTIVE/AIMS

Specific Aim 1 will establish case and control study cohorts with individualized timing of menstrual cycle phases as well as cycle-related psychological and physical symptoms. Participants with regular menstrual cycles will chart their symptoms and menstruation timing during **two menstrual cycles**. In addition, they will self-test LH surge for the purpose of estimating ovulation timing. This will generate two study cohorts: one with PMS/PMDD diagnosis and a healthy control with predictable bounds of menstrual cycle phases.

Specific Aim 2 will test differences in the gonadal and HPA axis hormones (measured at 8 individualized time points **in the second menstrual cycle**) between women with vs. without PMS/PMDD diagnosis.

Specific Aim 3 will test differences in stress reactivity between women with vs. without PMS/PMDD diagnosis. The stress reactivity procedure will be scheduled **in the second menstrual cycle**.

The duration of this research study is 4 years, starting November 2018 – November 2022.

4.0 ELIGIBILITY

Women between the ages of 18 and 35, with regular menstrual cycles lasting 21 to 35 days (Gingnell et al., 2013; Deng et al., 2018; Solis et al., 2008; Sohda et al., 2017) will be recruited for the study. They will be non-illicit drug using healthy individuals. Potential study participants who are not currently taking medications that affect central nervous system (CNS) or hormonal levels are eligible to participate in this study. They will also be asked to provide a breath sample to rule out smoking. They will be without past or current Axis 1 disorder (except anxiety or depression) or current anxiety or depressive disorder. Section 4.2 lists all the exclusionary criteria. Study participants will be recruited from the general population using electronic media (ex: Craigslist, UIC classifieds), flyers, and word-of-mouth referrals.

Research staff will assess eligibility criteria in an in-person screening visit based on a detailed flowsheet created specifically for this study. All research staff will be trained by the PI on assessing inclusion/exclusion criteria. Training logs will be securely stored and kept on file in the PI's laboratory. As the final approval of subject enrollment, study PI will sign off on all study participants who passed the screening session.

After completing each step of the screening and session flowsheet, research staff will mark time of completion and his/her initials. The PI will document approving participants for study participation on the flowsheet.

4.1 INCLUSION CRITERIA

- Female
- Aged 18-35 years
- Average menstrual cycle 21-35 days
- Access to smartphone compatible with Clearblue® Connected application for daily use

4.2 EXCLUSION CRITERIA

- Lifetime DSM-5 Axis 1 disorder (except anxiety and depression), as documented in the Mental Health Interview
- Current DSM-5 Axis depressive or anxiety disorder, as documented in the Mental Health Interview
- Positive urine drug screen test
- AUDIT > 8
- Self-reported smoker or carbon monoxide concentration ≥ 6 ppm
- Irregular menstrual cycle
- Current pregnancy (urine test-verified) or lactation, or a plan to become pregnant

- Moderate or high suicide risk
- Shipley IQ (vocabulary standard score) > 80
- Prescription medications that affect CNS and/or hormone levels
- Hormonal contraception (i.e. IUD or implant)
- Illicit Drug Use

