4.3 EXCLUDED OR VULNERABLE POPULATIONS

Vulnerable populations will not be included in the study. Participants who don't speak English are not included in the study because the questionnaires and study instructions have been developed in the English language.

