The first question of the initial survey is an auxiliary consent question. Individuals who answer "No" to the question "Does the CEDAR Lab have your consent to ask you questions regarding the PMSe Study?" will not be allowed to complete the initial survey. The initial survey contains questions about their substance use history to determine eligibility for the study as outlined in Sections 4.1 and 4.2. In the version 12 of the Protocol, the ACOG question was removed and included in the initial survey. Prospective participants who pass the initial survey will be scheduled for an in-person screening to determine eligibility for the study as outlined in Section 4.1 Inclusion Criteria and Section 4.2 Exclusion Criteria.

Data gathered from participants who fail to meet inclusion criteria will be kept with all study documentation in the event the same participant returns with information different than previously reported. In this event, research staff will be able to compare responses and optimize subject protection and study integrity. Following study completion, all data gathered from participants who failed screening criteria will be shredded with remaining study documentation.

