6.1 PROCEDURES AND ASSESSMENTS

Procedures and assessments occurring in each study phase is outlined in figure 2.

[figure not shown]
6.1A. SCREENING

Following the completion of the online survey, study participants will be scheduled for an in-person screening interview, at which time all the criteria listed in sections 4.1 and 4.2 will be assessed. Participants will also be instructed to complete a Demographics Survey during the screening. The purpose of the Demographics Survey is to compare the makeup of each experimental group and ensure that there is no significant demographic difference in the composition of the PMS/PMDD case vs. control group.

6.1B. MENSTRUAL CYCLE 1

The purpose of menstrual cycle 1 and 2 are to establish Premenstrual Syndrome diagnosis, Premenstrual Dysphoric Disorder diagnosis, or the healthy control status. Every day, participants will be asked to complete

the Daily Record of Severity of Problems (DRSP) (Endicott et al., 2006) in which they will chart their menstruation timing as well as give a score of 1 to 6 for affective or somatic symptoms according to their severity. Study physician, [name] (Assistant Clinical Professor of Psychiatry/Director of Addiction Psychiatry at UIC) will review DRSPs and provide Premenstrual Syndrome diagnosis when mean score 5 days before menstruation exceeds 50, mean luteal phase score is at least 30% higher than that of the follicular phase, and at least 3 symptoms score more than 3 in the 2-month period (see Deng et al., 2018, supplement). Otherwise, study participants will be classified as healthy controls. [name] role on the project is to provide the PMS or PMDD diagnosis as well as help with the recruitment of study participants. In addition, the study physician will be responsible for suicidality risk assessment (see Section 8.0).

6.1C. MENSTRUAL CYCLE 2

Table 2. Original Schedule of Study Visits According to Average Cycle Length

Average cycle length (days)	Visit 1 Menses	Visit 2 Mid follicular	Visit 3 Perioovulatory 1	Visit 4 Perioovulatory 2 ^a	Visit 5 Perioovulatory 3	Visit 6 Early luteal	Visit 7 Mid luteal	Visit 8 Late luteal
21	2	4	5	6	7	11	15	20
22	2	4	6	7	8	12	16	21
23	2	5	7	8	9	13	17	22
24	2	5	8	9	10	14	18	23
25	2	6	9	10	11	15	19	24
26	2	6	10	11	12	16	20	25
27	2	7	11	12	13	17	21	26
28	2	7	12	13	14	18	22	27
29	2	7	13	14	15	19	23	28
30	2	8	14	15	16	20	24	29
31	2	8	15	16	17	21	25	30
32	2	9	16	17	18	22	26	31
33	2	9	17	18	19	23	27	32
34	2	10	18	19	20	24	28	33

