8.0 DATA COLLECTION AND MANAGEMENT PROCEDURES

Data collection will occur throughout the 2-menstrual cycle study procedure. Table 5 outlines each of the data collection tools along with information when in the study they are collected.

Table 5. Questionnaires and physical measurements by visit type

Data Collection Tool	PRE-SCREENING	SCREENING	Menstrual Cycles 1 and 2 (DAILY)	Menstrual Cycle 2 VISIT 1	Menstrual Cycle 2 VISIT 2	Menstrual Cycle 2 VISIT 3	Menstrual Cycle 2 VISIT 4	Menstrual Cycle 2 VISIT 5	Menstrual Cycle 2 VISIT 6	Menstrual Cycle 2 VISIT 7	Menstrual Cycle 2 VISIT 8	ACUTE STRESS REACTIVITY STUDY
Initial Survey	✓											
Medication and Health Review		✓										
Shipley IQ Test		✓										
Mental Health Interview		✓										
Demographics Survey		✓										
Substance Use Survey		✓										
Physical Activity		✓										
State-Trait Anxiety Inventory (Y-2 only)		✓										
Beck’s Depression Inventory		✓										
Personality		✓										
Physical Measures*		✓										
Daily Record of Severity of Problems			✓									
Adverse Event Questionnaire				✓	✓	✓	✓	✓	✓	✓	✓	✓
Adverse Event Tracking Form				✓	✓	✓	✓	✓	✓	✓	✓	✓

Task Perception Rating												✓
Heart Rate			✓	✓	✓	✓	✓	✓	✓	✓	✓	✓
Computerized Cognition Tasks				✓	✓					✓	✓	
Visual Analogue Scale												✓
Blood Pressure												✓
Sleep Diary			✓	✓	✓	✓	✓	✓	✓	✓	✓	✓

*Includes: height; weight; blood pressure; pulse; sitting knee and abdominal height; waist, hip, abdominal, arm and thigh circumference.

Responses from Demographics, Physical Activity, Strait-Trait Anxiety Inventory (Y-2), Becks Depression Inventory, Personality, Physical Measurement, DRSPs, Task Perception Rating, VAS, Blood Pressure, Date of blood draws, Date of day 1 of cycle, and Date of ovulation surveys will be de-identified and submitted to NIH NIMH data repository. The repository will only be accessed by the PI and an assigned research staff on password protected computers.

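### The Shipley vocabulary criterion in Section 4.2 is reversed: as printed, only women scoring 80 or below are eligible

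*Combined protocol and SAP*

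**What the plan says.** Section 4.2 (Exclusion Criteria) includes the line "Shipley IQ (vocabulary standard score) > 80". Section 4.0 presents Section 4.2 as the full list of exclusions. Section 4.1 has four inclusion items: sex, age, cycle length and a compatible smartphone. None concerns IQ or vocabulary.

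The list is operative. Section 6.1A schedules an in-person screening interview "at which time all the criteria listed in sections 4.1 and 4.2 will be assessed". Section 4.0 adds: "Research staff will assess eligibility criteria in an in-person screening visit based on a detailed flowsheet created specifically for this study". The principal investigator signs off each woman who passes.

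The only other mention of the instrument is the row "Shipley IQ Test" in Table 5 (Section 8.0). It places the test at screening and gives neither a cut-off nor a direction.

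On the population, Section 4.0 says: "Study participants will be recruited from the general population using electronic media". It describes the women as healthy.

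**The concern.** A criterion in an exclusion list removes those who meet it. This one removes women with vocabulary scores above 80, so only those at 80 or below can enter. No passage gives a reason to study only low vocabulary scorers, and the rest of the protocol describes a different population.

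Both possible outcomes are a problem:

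- If staff followed the line, the study enrolled a population that Section 4.0 does not describe, and the target of 120 completers may be out of reach.
- If the flowsheet uses the opposite direction, women were enrolled against the printed protocol.

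A reader can guess the intent but cannot recover the exact rule. A reversed sign would mean excluding scores below 80. An inclusion requirement placed in the wrong list would mean excluding scores of 80 or below. The two differ for a score of exactly 80.

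**Working it through.** **Logic of the line.** The complement of excluding scores > 80 is admitting scores ≤ 80. The other numeric thresholds in Section 4.2 are AUDIT above 8 and carbon monoxide at or above 6 ppm. Both exclude high values, and both make sense as exclusions. The list therefore has one convention, and only the Shipley line gives an implausible result under it. Because the neighbouring signs read correctly, a fault in text extraction is unlikely, though it cannot be ruled out without the PDF.

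**Search for a correction.** Section 4.1 has no Shipley item. Sections 4.0, 5.0 and 6.1A refer back to the criteria without changing them. Table 5 gives no cut-off.

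**Fit with the rest of the protocol.** Section 5.0 requires that the woman can read and understands English before consent. Section 6.1C includes computerized tests of working memory, response inhibition and attention. Section 6.1d requires a five-minute speech and serial subtraction. A rule admitting only low vocabulary scorers sits badly with all of these.

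**Size, for illustration only.** The plan states no figure to reproduce and no score distribution, so a normal distribution is assumed.

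- Share kept = Φ((80 − mean)/SD).
- Mean 100, SD 15: Φ(−20/15) = Φ(−1.333) = 0.0912, so 90.9% are excluded.
- Mean 90, SD 16: Φ(−10/16) = Φ(−0.625) = 0.2660, so 73.4% are excluded.
- Mean 110, SD 12: Φ(−30/12) = Φ(−2.5) = 0.0062, so 99.4% are excluded.

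The last two are the extremes over means of 90 to 110 and SDs of 12 to 16.

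**Against the recruitment plan.** Section 9.0 gives about 1500 recruits and 120 completers, a yield of 120/1500 = 8.0%. The number who reach the Shipley test is not stated. It must be below 1500 if any women fail the online survey first, since Section 5.0 says: "Prospective participants who pass the initial survey will be scheduled for an in-person screening to determine eligibility". Taking 1500 as an upper bound:

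- Mean 100, SD 15: 1500 × 0.0912 = 136.8, or about 137 women left.
- Range over the assumed distributions: 1500 × 0.0062 ≈ 9 to 1500 × 0.2660 = 399.
- Room for every other loss at 100/15: 1 − 120/136.8 = 0.123. Other exclusions, anovulation and dropout together could remove at most 12.3% of those left.
- Number needed at the test at 100/15, before any other loss: 120/0.0912 ≈ 1316.

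**The case against.** Four points can be made in the plan's defence.

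1. **No passage states the intended rule**, so calling the direction wrong is an inference. That is true. The inference is strong, because nothing in the documents supports the literal reading.
2. **The population argument can be overstated.** Section 4.0 defines healthy through drug use, medication, smoking and psychiatric history, not vocabulary. Section 4.3 says "Vulnerable populations will not be included in the study" but does not define the term; the only group it names is non-English speakers. This stands in part: a low score does not contradict either statement outright. The consent, cognition and stress-task requirements are the better evidence, and they remain.
3. **The percentages depend on assumed distributions and chosen bounds.** This stands. Means of 95 to 110 with SDs of 10 to 15 would give 0.1% to 15.9% kept, rather than 0.6% to 26.6%. The 8.0% yield covers all losses and says nothing about which direction was intended. The defect does not depend on any of these numbers.
4. **Literal application is unlikely.** Staff are trained by the investigator, use a dedicated flowsheet and need sign-off. These safeguards lower the risk that the line was followed, but they do not correct the text. If they worked, the protocol and actual practice disagree.

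No endpoint, group definition or analysis uses this line.

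**Conclusion.** The concern holds. As printed, an operative eligibility criterion admits only women with a Shipley vocabulary score of 80 or below, and nothing in the documents corrects it. That this is unintended is a strong inference, not a stated fact. If the line were applied literally, it would exclude 90.9% of women tested under the assumed 100/15 normal distribution, with 73.4% to 99.4% over the main range examined. These figures show scale only.

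Whether the error reached practice cannot be judged without the flowsheet, so the effect on recruitment is conditional. The power calculation in Section 12.0 does not depend on this line. It must be fixed because a selection rule that staff are told to assess is wrong as written.

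**What to change.** 1. Confirm the intended rule, and compare Section 4.2 with the screening flowsheet to establish which rule was used.
2. Amend Section 4.2 so that low scores are excluded. State whether the cut-off is < 80 or ≤ 80, so that a score of exactly 80 has one defined outcome. Reconcile the flowsheet if it differs.
3. Check stored Shipley scores against the enrolment decisions for women already tested, including those who failed screening, and document any departure from the printed protocol.

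The third step is time-sensitive. Section 5.0 says: "Following study completion, all data gathered from participants who failed screening criteria will be shredded with remaining study documentation". Section 3.0 gives a planned end of November 2022, so the first question is whether the records are still held.

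The cost is a one-line amendment, one comparison of two documents, and a review of records already collected. No new data are needed and the sample size does not change.

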4.3 EXCLUDED OR VULNERABLE POPULATIONS

Vulnerable populations will not be included in the study. Participants who don't speak English are not included in the study because the questionnaires and study instructions have been developed in the English language.

5.0 SUBJECT ENROLLMENT

Study participants will be recruited from the general population using electronic media (ex: Craigslist, UIC classifieds, social media), flyers, and word-of-mouth referrals. One paper flyer and one electronic flyer (attached to this application) will be distributed. The telephone number and email of the CEDAR Lab will be included in paper and electronic advertisements. Prospective participants will contact the lab to complete an initial screening survey in REDCap (see attached "Initial Survey"). All contact with participants will be conducted through the lab's UIC email address or UIC office phone number. Participants who email the lab will be sent an introductory email outlining study goals and directed to fill out the REDCap survey. Participants who phone the lab will be asked to provide an email address, following which lab personnel will send the introductory email.

Additionally, CEDAR Lab will obtain identified data from CCTS CRDW - UIC CIRCLE specifically for the purpose of recruiting potential participants with premenstrual dysphoric disorder (PMDD). The requested data set will include names, email addresses, telephone numbers, street address, city, and state for females between ages 18-35 with PMDD diagnosis (ICD-10-CM F32.81 or ICD-9-CM 625.4). Lab personnel will telephone or send an introductory email to potential participants outlining study goals and inviting those interested to fill out the REDCap survey. If lab personnel are unable to reach potential participants by email or telephone, a letter will be sent out through mail with information regarding the study using the address provided in the data set. Study personnel will follow the attached "Screening Script" for communications with participants that occur prior to their in-person consent.

CEDAR Lab will use the following online research study posting systems for recruiting participants: ResearchMatch.org, UI Health Research Registry, and The New Normal Match. Interested volunteers may communicate through the online research study posting systems. Volunteers of interest will be contacted with an introductory email via the respective portal.

The first question of the initial survey is an auxiliary consent question. Individuals who answer "No" to the question "Does the CEDAR Lab have your consent to ask you questions regarding the PMSe Study?" will not be allowed to complete the initial survey. The initial survey contains questions about their substance use history to determine eligibility for the study as outlined in Sections 4.1 and 4.2. In the version 12 of the Protocol, the ACOG question was removed and included in the initial survey. Prospective participants who pass the initial survey will be scheduled for an in-person screening to determine eligibility for the study as outlined in Section 4.1 Inclusion Criteria and Section 4.2 Exclusion Criteria.

Data gathered from participants who fail to meet inclusion criteria will be kept with all study documentation in the event the same participant returns with information different than previously reported. In this event, research staff will be able to compare responses and optimize subject protection and study integrity. Following study completion, all data gathered from participants who failed screening criteria will be shredded with remaining study documentation.

The consent procedure is detailed according to processes established in the Code of Federal Regulation and the University of Illinois Institutional Review Board. All research staff responsible for screening participants will be trained by the PI and document screening protocol in the Screening Flowsheet. The informed consent procedure will be carried out in a private and a quiet setting. Prior to initiating the procedure, the person consenting will ensure that the individual is an adult, is able to read, and understands the English language. The most recent version of the ICD will be used. The individual obtaining consent will briefly summarize each section of the ICD. Non-resident alien status will be ascertained and will be confirmed during the consent process. Study participants will be informed that the payments must be processed in accordance with the section “Will I be reimbursed for any of my expenses or paid for my participation in this research study?” of the informed consent form. Non-resident aliens who cannot provide the appropriate documents to receive payments will not be eligible to participate in the study. Study participants will be given ample time to review the document and encouraged to ask clarifying questions. Questions will be noted in the ICD by research staff. Participants who do not accept the use of the Clearblue Connected application on their compatible smartphone will not be allowed to participate in the study. The participant will be provided with a signed copy of the ICD.

